## **Study Protocol**

The purpose of this project is to assess a self-paced online program, *Media Aware Parent: Tween (MAP: Tween)*, designed to provide parents with knowledge about preadolescent development, media mediation skills, and practice in high-quality parent-child communication about body image, sexual development, gender stereotypes, and romantic relationships. The program will help parents of preadolescents (9-12 years of age) have effective conversations with their child about these topics and enhance media literacy skills to counter unhealthy media messages.

Study participants will contribute to the evaluation of a web-based application that will act as a resource for parents to have informed high-quality conversations with their preadolescent child about body image, sexual development, gender stereotypes, and romantic relationships. Through their participation, parents and children in the study may also acquire an increased knowledge about these topics and media literacy.

Preadolescence is a critical stage of development as youth transition from childhood into adolescence, and the *MAP: Tween* program may help improve communication between parents and children. High-quality parent-child communication has been shown to positively impact youth decision-making and health outcomes; therefore, this program has the potential to benefit society by resulting in an evidence-based program to enhance parent-child communication.

The procedure that will be used for conducting the research study is as follows:

1. We will aim to recruit a diverse sample of 300 parent-tween pairs (youth aged 9-12) to participate in this study. We will aim to have the sample consist of at least 40% fathers or male guardians and no more than 60% non-Hispanic/Latinx white adult participants. Parent-child pairs will be stratified by parent's gender and race/ethnicity prior to randomization to ensure diversity across groups.
2. A recruitment website will be available. Interested parents can complete an online screener found on the website. If eligible, parents will be directed to a place where parents and their children can complete the online informed consent process.

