3. On the parent permission and consent form, participants will be asked for their preferred email address to receive study communications over the study period. Before receiving communications at this address, they will need to verify that they can receive emails at this address by clicking a link that is emailed to them. Parents will also be asked on the permission and consent form to agree to receiving study communication via text. Before receiving text communications at their phone number, they will need to verify that they can receive texts at their number by clicking on the verification link that is sent via SMS message. Finally, parents will also be asked to verify their name and address either through uploading on the permission-consent form an image of some form of document that includes their name and address (e.g., license; electric bill) or showing the document to a study team member through a live web conferencing call (e.g., Zoom call). [Modification: Due to concerns of people uploading images of documentation that was photoshopped, during the study the verification protocol was modified (and approved by the IRB) so that all participants were asked in the screener survey to indicate the school district where their

child attended school and then this was checked against our list of schools that distributed our flyer. Only parents that listed a school district where our flyer was distributed, were enrolled.]

4. The study team will enroll eligible, consented, and verified pairs based on whether there is room in the study according to gender and race/ethnicity stratification. If there is space in the study, parent-child pairs will be randomly assigned to either the Intervention condition (receiving the *MAP: Tween* program) or the Active Control condition (i.e., receiving medically-accurate information from sources like the CDC about topics such as preadolescent development, body-image, gender, and relationship health).
5. Pretest questionnaires for parents and their children will be distributed to enrolled parents in two separate emails/texts containing a link to complete their respective questionnaires. Participants will have one week to complete their questionnaires. If both the parent and child complete their questionnaire, they will be eligible for a \$30 gift card.

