## **Statistical Analysis Plan**

Preliminary Analyses. Psychometric analyses will be conducted to study the reliability, validity, and distributions of key variables. These analyses will be conducted by first assessing the internal consistency (i.e., Cronbach's alphas) of outcomes with Likert-type scales. If the alpha for an outcome is unacceptable (i.e., less than 0.70), then items that do not correlate strongly with the total scale will be removed, one-at-a-time, until the alpha for the scale is acceptable. Once items are averaged together to create the scale, outcome distributions will be assessed using univariate analyses to examine skewness and kurtosis, providing preliminary insight into potential deviations from normality prior to model fitting. If outcomes are unacceptably skewed or kurtotic, then outcomes scales will be modified (via re-scaling or dichotomizing) or eliminated

from analysis. The impact of random assignment on producing equivalent groups will be assessed on pretest demographic and background characteristics in a series of t-tests and  $\chi^2$  analyses. If we establish that the groups are not equivalent on any pre-specified variables, these variables will be used as covariates in the analyses of intervention effects. For continuous outcomes, normality assumptions will be tested using the Shapiro-Wilk test, Q-Q plots, and histogram of the residual distributions, via linear regression analyses of raw data, with all covariates included in the model. If the Shapiro-Wilk test is significant (p-value of  $w < .05$ ), the histogram of residuals deviates substantially from a bell curve, and the Q-Q plot includes a pronounced S-curve (deviates substantially from the line), then the outcome scale will be transformed (via re-scaling or dichotomizing) or eliminated from analyses. Finally, we will use multiple imputation to handle missing data and analyses will be conducted on each imputed dataset, with resulting estimates and standard errors pooled using Rubin's Rules.

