**Main Analyses.** Analyses will examine the effects of the program on attitudes, cognitions, and behaviors, which will provide information on program feasibility. We will use a series of linear regressions for outcomes with continuous distributions and logistic regressions for dichotomous (yes/no) outcomes in intent-to-treat analyses. Posttest scores will be regressed onto pretest scores, covariates, and the intervention effect. Covariates will include those that were non-equivalent between groups at pretest, parent sex, child sex, socioeconomic status, and parent- and child-reported supportive parenting. The Benjamini-Hochberg procedure will be employed to control for the False Discovery Rate (FDR).

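### Race/ethnicity is used to stratify randomization but is not a fixed covariate in the outcome models: a small, avoidable misalignment of design and analysis

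*Combined protocol and SAP*

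**What the plan says.** Step 1 of the Study Protocol sets the design: "Parent-child pairs will be stratified by parent's gender and race/ethnicity prior to randomization to ensure diversity across groups". Step 4 uses the same two factors to control entry, since pairs are enrolled "based on whether there is room in the study according to gender and race/ethnicity stratification" and then randomly assigned.

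The Main Analyses paragraph of the Statistical Analysis Plan regresses posttest on pretest, covariates and the intervention effect, with linear models for continuous outcomes and "logistic regressions for dichotomous (yes/no) outcomes". Its covariate rule is: "Covariates will include those that were non-equivalent between groups at pretest, parent sex, child sex, socioeconomic status, and parent- and child-reported supportive parenting". Race/ethnicity is not named.

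The Preliminary Analyses paragraph gives the only other way in, after t-tests and χ² tests on pretest characteristics: "If we establish that the groups are not equivalent on any pre-specified variables, these variables will be used as covariates". The pre-specified variables are not listed and no threshold for non-equivalence is given. The same paragraph says "we will use multiple imputation to handle missing data" but does not list what the imputation model contains.

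**The concern.** Of the two factors used to stratify, one is in the model (gender, as parent sex) and the other is not, and the plan gives no reason. The baseline comparison does not fill the gap. It responds to imbalance between arms, which stratification is meant to remove, and says nothing about whether the factor predicts the outcome. A factor the design has balanced will therefore seldom be selected, however prognostic it is.

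What is at stake depends on how pairs are allocated within strata, which the documents do not state:

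- **Linear models, blocked within strata.** The effect estimate is already balanced on race/ethnicity, so its true variability is the same with or without the covariate. Omitting the covariate leaves its variance in the residual. The reported standard error is too large, intervals are too wide and tests are mildly conservative.
- **Linear models, simple assignment.** The standard error is valid, but precision that adjustment would recover is lost.
- **Logistic models.** The standard error is not inflated. Omission pulls the conditional log-odds ratio toward zero, with a small loss of power.

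If race/ethnicity does not predict posttest given the pretest score and the listed covariates, none of this costs anything.

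**Working it through.** The plan gives no power calculation, so there is no stated figure to reproduce.

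**Inputs from the documents.** The recruitment aim is 300 pairs in two arms, with at least 40% fathers or male guardians and at most 60% non-Hispanic/Latinx white adults (Study Protocol, steps 1 and 4). The fixed covariates are as listed above.

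**Assumptions.** 1:1 allocation; two-sided α = 0.05 for a single outcome; baseline comparison at 0.05; an effect that gives 80% power when race/ethnicity is in the model, which is (1.960 + 0.842) × √(2/150) = 0.323 residual SD; partial R² of race/ethnicity, given the other covariates, from 0 to 10%. Multiple imputation and the Benjamini-Hochberg step are not modelled.

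**Formulas.** Let k = 1/√(1 − R²), the factor by which the residual SD grows when race/ethnicity is left out.

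- Blocked (true SD of the estimate unchanged, reported SE multiplied by k): type I error = 2[1 − Φ(1.96k)]; power = Φ(2.802 − 1.96k); equivalent pairs = 300 × {[(1.96k + 0.842)/2.802]² − 1}.
- Simple (SE valid): power = Φ(2.802/k − 1.96); equivalent pairs = 300/(1 − R²) − 300.

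**Worked line, R² = 5%.** k = 1.0260 and 1.96k = 2.011.

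- Blocked: type I error 2[1 − Φ(2.011)] = 4.4%; power Φ(2.802 − 2.011) = Φ(0.791) = 78.5%; pairs 300 × [(2.853/2.802)² − 1] = 11.
- Simple: power Φ(2.731 − 1.96) = Φ(0.771) = 78.0%; pairs 300/0.95 − 300 = 15.8, or 16.

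| Partial R² | k | Blocked: SE too large by | Blocked: type I error | Blocked: power | Blocked: pairs | Simple: power | Simple: pairs |
|---|---|---|---|---|---|---|---|
| 0% | 1.0000 | 0% | 5.0% | 80.0% | 0 | 80.0% | 0 |
| 1% | 1.0050 | 0.5% | 4.9% | 79.7% | 2 | 79.6% | 3 |
| 2% | 1.0102 | 1.0% | 4.8% | 79.4% | 4 | 79.2% | 6 |
| 5% | 1.0260 | 2.6% | 4.4% | 78.5% | 11 | 78.0% | 16 |
| 10% | 1.0541 | 5.4% | 3.9% | 76.9% | 23 | 75.7% | 33 |

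**Simulation of the linear case** (300 pairs, two-level race/ethnicity, 4,000 trials per scenario, R² = 10%):

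- Blocks of 4 within strata, no treatment effect: mean model SE 0.122 without race/ethnicity and 0.116 with it; empirical SD of the estimate 0.115 either way; type I error 3.6% without and 4.8% with. With the treatment effect, power was 76.5% and 79.8%.
- Unstratified 1:1 assignment, with the treatment effect: power 74.6% never adjusting, 75.0% under the planned test-then-adjust rule and 78.7% always adjusting. The baseline comparison recovers little of the loss.

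**How often the baseline comparison selects race/ethnicity** (4,000 allocations):

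- Two levels, blocks of 4 or 8: 0.0%.
- Five levels (assumed 60/15/15/6/4%) tested while the strata use two levels: 1.9% with blocks of 4 and 2.2% with blocks of 8.
- Simple assignment: 5.3% with two levels and 5.0% with five.

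**Logistic case** (blocked, treatment log-odds ratio 0.70, 10,000 runs per cell):

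| Race/ethnicity log-OR | Mean estimate, without / with | Power, without / with |
|---|---|---|
| 0 | 0.704 / 0.707 | 85.7% / 85.9% |
| 0.5 | 0.698 / 0.711 | 84.7% / 85.3% |
| 1.0 | 0.667 / 0.710 | 82.4% / 83.8% |

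At log-OR 1.0 the SE is 0.235 without and 0.244 with, and type I error is 4.6% and 5.2%. Under simple assignment, power is 80.8% without and 82.8% with. The log-odds ratios are assumed, and the results also depend on the event rate, which the documents do not give. They show direction and order of size only.

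**The case against.** The strongest objection is size. The pretest score, socioeconomic status, both sexes and two supportive-parenting measures are already in the model, and posttest follows pretest by about four weeks. A partial R² of 10% on top of these would be surprising, and at 1% to 2% the loss is under one power point, or 2 to 6 pairs. That stands. This is a refinement, and nothing in the documents shows that the loss is more than negligible.

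Second, under blocking the estimator itself is not less precise; only its reported standard error is too large. That also stands, so the loss there is one of interval width and power.

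Third, stratification here might mean only recruitment quotas. Step 4 can be read that way, although step 1 gives the purpose as "gender and race/ethnicity prior to randomization to ensure diversity across groups". If quotas are all that is meant, the simple-assignment columns apply and fixed adjustment still gains precision.

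Fourth, selection rates near 5% presuppose a 0.05 threshold that the plan does not state. That is correct, and another threshold would move the rate. It would not make the comparison a test of prognostic value.

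Fifth, many racial/ethnic categories could leave sparse cells and unstable logistic fits; a 4% group is about 12 of 300 pairs. Using the categories that defined the strata limits this risk. They are not documented and need to be stated.

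**Conclusion.** The point holds as a minor matter of efficiency and of matching analysis to design. Race/ethnicity is a stratification factor, it is absent from the fixed covariates, and its only route into the models is a comparison that will rarely select it.

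Type I error is not inflated. The linear tests are at nominal level or conservative. In the logistic models, a null treatment effect remains null whether or not the factor is included.

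The power cost in the linear models ranges from nothing, through about half a point to two points at a partial R² of 2% to 5%, to three or four points at 10%. These figures assume 300 analyzed pairs, 1:1 allocation, a single test at 0.05 and 80% power with the covariate included. The partial R² values are assumptions, as the documents give no estimate.

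**What to change.** Add to the Main Analyses paragraph: *Race/ethnicity, in the categories used for the randomization strata, is a fixed covariate in every linear and logistic outcome model and is included in the multiple-imputation model, whatever the baseline comparison shows.* It belongs in the imputation model because every variable in the analysis model should be there.

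State those categories, and code the parent sex/gender covariate as it was coded for stratification; the Study Protocol says gender and the analysis plan says sex.

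The cost is one sentence and one to a few degrees of freedom out of about 300. No new data are needed, because race/ethnicity is already used for enrollment. The change should be dated before outcomes are examined by arm. If that point has passed, report the models with and without race/ethnicity and say which was pre-specified.

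### Child age is left out of the fixed covariates in a trial defined by ages 9-12; adding it is a small, low-cost gain in precision and pre-specification, not a correction of bias

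*Combined protocol and SAP*

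**What the plan says.** The Study Protocol sets the sample by child age: "We will aim to recruit a diverse sample of 300 parent-tween pairs (youth aged 9-12) to participate in this study". Its opening section gives a developmental rationale: "Preadolescence is a critical stage of development as youth transition from childhood into adolescence". Step 1 names the stratification factors: "Parent-child pairs will be stratified by parent's gender and race/ethnicity prior to randomization to ensure diversity across groups". Step 2 adds that "Interested parents can complete an online screener found on the website", without listing what the screener asks.

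In the SAP, Main Analyses gives the model, "Posttest scores will be regressed onto pretest scores, covariates, and the intervention effect", and the covariates: "Covariates will include those that were non-equivalent between groups at pretest, parent sex, child sex, socioeconomic status, and parent- and child-reported supportive parenting". Besides the pretest score there are five fixed covariates (parent sex, child sex, socioeconomic status, and supportive parenting as reported by each member of the pair) and one conditional class.

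Preliminary Analyses describes how that class is filled. Equivalence of the groups "will be assessed on pretest demographic and background characteristics in a series of t-tests and" chi-squared analyses, and pre-specified variables found non-equivalent become covariates. The SAP neither lists those variables nor gives the threshold for non-equivalence.

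**The concern.** Children of 9 and of 12 sit at different points of the transition that the protocol describes, so age is a plausible predictor of at least some outcomes. The plan fixes child sex as a covariate but not child age, and gives no reason for the difference.

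Three things follow:

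- **Precision.** If age predicts posttest after the pretest score is accounted for, leaving it out keeps that variation in the residual and widens the intervals of the linear models.
- **Chance imbalance.** An age difference between arms that falls short of the balance-test threshold stays in the estimate without adjustment.
- **Pre-specification.** Whether age is in the model is not known until the balance tests have been run, and then depends on an unlisted set of variables.

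The pretest score removes much of any stable age difference in level. It does not remove age-related change between the two questionnaires, nor the part of true level that the pretest measures with error.

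**Working it through.** The documents contain no power calculation, effect size or age-outcome correlation, so there is no stated figure to reproduce. What follows is an illustration.

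**Inputs from the documents:** 300 pairs; ages 9-12; each posttest adjusted for its pretest; posttest about four weeks after pretest (Study Protocol, step 8).

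**Assumptions:** 150 pairs per arm (no ratio is stated) with no loss; ages spread evenly over 9, 10, 11 and 12; an age slope of 0.1 to 0.2 residual SD per year after pretest adjustment; two-sided 5% for the balance test and the treatment test.

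1. *SD of age:* the variance of {9, 10, 11, 12} is 1.25, so SD = √1.25 = 1.118 years.
2. *Residual variance removed:* slope² × 1.25. At 0.1 this is 0.0125 (1.25%); at 0.2 it is 0.05 (5%). The corresponding partial correlations are 0.1 × 1.118 = 0.11 and 0.2 × 1.118 = 0.22.
3. *Effect on the standard error (linear models):* √(1 − 0.0125) = 0.994, a fall of about 0.6%; √(1 − 0.05) = 0.975, a fall of about 2.5%.
4. *Equivalent sample size:* 300/0.9875 = 303.8 and 300/0.95 = 315.8, or about 4 to 16 extra pairs.
5. *Imbalance that would pass the test:* the SE of the arm difference in mean age is 1.118 × √(2/150) = 0.129 years, and 1.96 × 0.129 = 0.25 years. The shift in the effect estimate is 0.25 × 0.1 = 0.025 to 0.25 × 0.2 = 0.05 residual SD.
6. *Scale of that shift:* the SE of the treatment effect is √(2/150) = 0.115 residual SD, so the shift is 0.025/0.115 = 0.22 to 0.05/0.115 = 0.43 of one SE. This is the extreme at the threshold. The expected absolute age difference is 0.129 × √(2/π) = 0.10 years, which gives a shift of 0.01 to 0.02 SD.

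**Cross-check from raw correlations.** Let a be the age-outcome correlation, taken as equal at both waves, and ρ the pretest-posttest correlation. The partial correlation of age with posttest given pretest is

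r = a(1 − ρ) / √[(1 − a²)(1 − ρ²)].

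| a | ρ | r | Fall in SE | Power, from 80% without age |
|---|---|---|---|---|
| 0.2 | 0.8 | 0.07 | 0.2% | 80.2% |
| 0.3 | 0.6 | 0.16 | 1.2% | 81.0% |
| 0.4 | 0.5 | 0.25 | 3.2% | 82.5% |

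The 80% base corresponds to an effect of 0.323 residual SD at 150 per arm. The slopes assumed above (r = 0.11 to 0.22) lie inside this range. The upper slope is demanding: r = 0.22 needs a of about 0.36 when ρ = 0.5, and about 0.47 when ρ = 0.7.

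**The case against.** The strongest reply is that nothing here is an error. The plan has a fixed covariate list and a pretest score, and the choice of one further covariate is partly a matter of preference. With about four weeks between questionnaires, the pretest should absorb most stable age differences. Age is also an obvious demographic, so the non-equivalence rule may already bring it in. Finally, chance age imbalance is already part of the width of an unadjusted interval, so it should not be counted as a second harm on top of lost precision. All of this stands, and it limits the point to a small one.

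What it does not answer is the planning gap. The rule acts only after a balance test, on variables that are not listed, so it cannot deliver a planned precision gain and leaves sub-threshold imbalance alone.

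A reader might infer more than the documents support:

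- *That omitting age biases the treatment effect.* Under randomisation it does not, on average, in the linear models.
- *That chance age imbalance is wholly unaddressed.* The non-equivalence rule addresses it in part.
- *That the screener is stated to record age.* This is a fair inference from the age range, but it is not written.
- *That the outcomes are known to depend on age.* The developmental topics are listed as program content; Main Analyses describes outcomes only in broad classes, and no scale or scale length is given.
- *That every model gains precision.* The variance arithmetic applies to linear regression. In the logistic models, adding age makes the odds ratio conditional on age, and its interval need not narrow.

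**Conclusion.** The point holds as a minor improvement to precision and pre-specification. Child age is neither a stratification factor nor a fixed covariate, and its only way into the models is conditional and incompletely specified. This is not a threat to validity.

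For continuous outcomes the likely gain is a standard error smaller by about 0.6% to 2.5%. That rests on an assumed slope of 0.1 to 0.2 residual SD per year, an even age spread and 150 pairs per arm. The documents cannot establish the slope. At a slope of zero nothing is gained and one degree of freedom is spent.

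**What to change.** In Main Analyses, add child age in years, as recorded at enrolment, to the fixed covariates for all outcomes, whatever the pretest balance test shows. In Preliminary Analyses, name it among the variables in the multiple-imputation model. State that in the logistic models the odds ratio is conditional on age as well as on the other covariates.

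The cost is a phrase in each of two SAP paragraphs and one degree of freedom per model. No new measurement should be needed, provided that age is recorded when eligibility is checked; the sponsor should confirm this.
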